### **9.4.3 Analysis of the Secondary Endpoint(s)**

Descriptive analysis techniques will be used to characterize clinical characteristics of the study participants, and incidence of adverse events and change in secondary exploratory outcomes. Center and variability of continuous variables will be presented as means (SD) when they follow a normal distribution and as medians and interquartile range otherwise. Log transformation will be applied on variables with skewed distribution

CONFIDENTIAL

This material is the property of the NYU School of Medicine and Langone Medical Center. Do not disclose or use except as authorized in writing by the study sponsor  
Interventional Template Version: 28 APR 2017

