## **9.2 Statistical Hypotheses**

Primary Feasibility Objective: The null hypothesis for the primary feasibility objective is that 75% of the subjects will successfully complete ferumoxytol injection treatment as per study protocol.

CONFIDENTIAL

This material is the property of the NYU School of Medicine and Langone Medical Center. Do not disclose or use except as authorized in writing by the study sponsor  
Interventional Template Version: 28 APR 2017

There are no hypotheses to be tested for the primary safety objective and exploratory secondary objectives. Descriptive statistics will be used to analyze these data. The purpose of the analyses is to obtain estimates of the study treatment risk in the study population, and the magnitude and variance of change in the exploratory endpoints in the study population. These pilot data will be useful for planning of future clinical trials.

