### **9.4.2 Analysis of the Primary Efficacy Endpoint(s)**

Chi-Square analysis will be used to compare the observed proportion of successful completion of ferumoxytol injection treatment with the null hypothesis of 0.75. Statistical significance will be inferred for one-tailed p-value <0.05.

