#### **9.5 Sample Size**

The null hypothesis for the primary feasibility objective is that 75% of the subjects will successfully complete ferumoxytol injection treatment as per study protocol. 20 subjects will provide >80% power (one-tailed alpha=0.05) to detect <40% successful completion of ferumoxytol injection treatment.

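### The reporting rule in 9.4.3 plans no mean or SD on the measured scale for a change judged non-normal, although 9.2 says these analyses are to estimate the variance of change

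*Combined protocol and SAP*

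**What the plan says.** Section 9.2 sets no hypotheses for the safety and exploratory objectives. It gives the purpose of those analyses as estimating treatment risk and "the magnitude and variance of change in the exploratory endpoints in the study population", and adds: "These pilot data will be useful for planning of future clinical trials".

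Section 9.4.3 then fixes the output. Its scope includes "incidence of adverse events and change in secondary exploratory outcomes", so it covers the changes in ferritin, transferrin saturation, hemoglobin and six-minute walk distance. Continuous variables are to be "presented as means (SD) when they follow a normal distribution and as medians and interquartile range otherwise". The next sentence reads "Log transformation will be applied on variables with skewed distribution". Section 9.4.4 and the Statistical Analysis row of the Protocol Summary repeat the same text.

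No section names a test or criterion for normality, and none asks for the mean and SD of change whatever the distribution.

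**The concern.** The stated purpose names a variance, but the reporting rule makes that variance conditional. If a change is judged non-normal, the planned summary is a median and IQR, and a later planner reading the report has no SD of change to use. Rebuilding one from the IQR means assuming the normality that was just rejected. With skewed or heavy-tailed data that tends to give an SD that is too small, and so a later trial that is too small.

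The switch also depends on an undefined judgement made on 20 subjects or fewer, since section 5.7.2 does not replace withdrawals and follow-up values come only from routine chart data. Two endpoints with the same underlying shape could be reported differently.

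**Working it through.** **The plan's own figure.** The only sample-size statement is "20 subjects will provide >80% power (one-tailed alpha=0.05) to detect <40% successful completion of ferumoxytol injection treatment", for the test that will "compare the observed proportion of successful completion of ferumoxytol injection treatment with the null hypothesis of 0.75". With n = 20, 11 completers give z = (0.55 − 0.75)/√(0.75 × 0.25/20) = −2.07, one-tailed p = 0.019. Twelve completers give p = 0.061. The rule is therefore to reject at 11 or fewer. Exact binomial: P(X ≤ 11 | 0.75) = 0.041 and P(X ≤ 11 | 0.40) = 0.943. The claim of more than 80% power reproduces, and nothing below changes it.

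**Inputs for this point.** n = 20 (section 9.5) and the rule in 9.4.3 are from the plan. The plan supplies no normality test and no distribution for the changes. Shapiro-Wilk at 5% and the shapes below are assumptions.

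**Step 1: how often the rule would drop the mean and SD.** Simulated at n = 20. Skewness is 2/√shape for the gamma and (e^{s²} + 2)√(e^{s²} − 1) for a lognormal with log-SD s.

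| Assumed shape of the change | Skewness | Flagged non-normal |
|---|---|---|
| Normal | 0 | 5% |
| Lognormal, log-SD 0.3 | 0.95 | 23-25% |
| Gamma, shape 4 | 1.0 | 29% |
| Lognormal, log-SD 0.5 | 1.75 | 52% |
| Lognormal, log-SD 0.75 | 3.3 | 80% |
| Lognormal, log-SD 1.0 | 6.2 | 93% |
| t, 4 df (symmetric, heavy-tailed) | – | 24% |

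If all four changes were truly normal and independent, at least one would still lose its mean and SD with probability 1 − 0.95⁴ = 18.5%.

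**Step 2: what the median and IQR leave a planner.** The usual conversion is SD ≈ IQR/1.349, which is exact only under normality. Among flagged samples:

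| Shape | Median of (IQR/1.349)/true SD | Implied N, as share of N needed (ratio²) | Median of sample SD/true SD |
|---|---|---|---|
| Lognormal 0.5 | 0.76 | 57% | 1.05 |
| Lognormal 0.75 | 0.61 | 38% | 0.91 |
| Lognormal 1.0 | 0.45 | 20% | 0.76 |
| t, 4 df | 0.66 | 44% | 1.10 |

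The sample SD is itself imperfect under strong skew, but it is much closer than the rebuilt value.

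For scale, take the first hemoglobin trial in Table I of section 2.4.2: difference 0.82 − 0.16 = 0.66 g/dL, with SD 1.24 assumed in both arms. At two-sided 5% and 80% power, N per arm = 2(1.960 + 0.842)² × 1.24²/0.66² = 55.4, so 56. An SD understated by an illustrative factor of 0.70 gives 55.4 × 0.49 = 27.2, so 28 per arm, and the true power is then 51%.

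**Step 3: does the log sentence supply the variance?** It does not say whether raw values or changes are logged, or what is then reported. A change cannot be logged where it is zero or negative. If hemoglobin changes were normal with the three ferumoxytol means and SDs in Table I, the share at or below zero would be Φ(−0.82/1.24) = 25%, Φ(−1.22/1.25) = 16% and Φ(−1.02/1.13) = 18%. The sentence also leaves a skewed variable with two treatments, median and IQR or a log-scale summary, and no rule for choosing between them.

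**Step 4: is a multiplier on the SD a safe remedy?** The upper one-sided 80% limit from the chi-square formula at n = 20 is √(19/χ²₀.₂₀,₁₉) = 1.18 × SD. Its simulated coverage of the true SD is 80% for normal data, 72% for gamma shape 4, and 61%, 50% and 37% for lognormal log-SD 0.5, 0.75 and 1.0. It fails in exactly the cases at issue.

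**The case against.** The plan does address skewness. If the log sentence means that raw laboratory values are logged before differencing, a log-scale mean and SD of change could be reported, and that is a variance of a kind. So it would be too strong to infer that a skewed endpoint gets a median and IQR and nothing else. What stands against the plan is that this reading has to be supplied by the reader and still gives nothing on the measured scale.

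A reader might also infer that the pilot exists to estimate variance. It does not: feasibility is the primary objective (sections 3.1 and 9.4.1), and 9.2 states the purpose of the safety and exploratory analyses only, with treatment risk alongside. Nor is all information on spread lost, since a median change is a magnitude and an IQR is a measure of spread.

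Another tempting reading is that the reporting format would be close to arbitrary. Under the assumed test the flag rises from 5% to 93% as skewness grows. It is unstable for mild to moderate skew, not everywhere, and the documents name no test at all.

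Finally, one might infer that a later trial sized on the bare pilot SD is more likely than not to be too small. For normal data the sample SD falls below the true SD in about 54-55% of pilots (n = 20 and an assumed n = 15), barely more than half. Nothing in the documents says a planner would use the SD without allowance. Individual data are held in REDCap and retained (sections 13.1 and 13.2), so mean and SD can be computed whenever they are wanted.

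**Conclusion.** The mismatch between 9.2 and 9.4.3 is real but narrow. Followed as written, the rule can leave out, on the measured scale, the mean and variance of change that the analyses are meant to estimate, and neither the IQR nor the log sentence reliably supplies them. It is a minor point. The change endpoints are descriptive, the criterion "Statistical significance will be inferred for one-tailed p-value <0.05" applies to the feasibility test alone, and no sample size or primary result moves.

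The gap itself follows from the text. The flagging rates and the understatement of a rebuilt SD rest on an assumed test and assumed shapes; they show the direction and rough size of the effect and are not forecasts for this trial.

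**What to change.** Replace the conditional rule in 9.4.3, and align the repeated text in 9.4.4 and the Protocol Summary, along these lines:

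*For each of the four change endpoints (serum ferritin, transferrin saturation, hemoglobin, six-minute walk distance), the number of subjects, mean change with 95% confidence interval, standard deviation, median and interquartile range will be reported on the original scale regardless of distribution. Any log-scale summary will be additional, and the quantity transformed will be stated.*

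Do not prescribe a fixed multiplier such as 1.18 × SD. If an interval for the SD is shown, label it as assuming normality or use a method that does not.

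The cost is a few extra table columns. No new data, visits or subjects are needed.

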#### **9.4.4 Safety Analyses**

Descriptive analysis techniques will be used to characterize clinical characteristics of the study participants, and incidence of adverse events and change in secondary exploratory outcomes. Center and variability of continuous variables will be presented as means (SD) when they follow a normal distribution and as medians and interquartile range otherwise. Log transformation will be applied on variables with skewed distribution

#### **9.5 Sample Size**

The null hypothesis for the primary feasibility objective is that 75% of the subjects will successfully complete ferumoxytol injection treatment as per study protocol. 20 subjects will provide >80% power (one-tailed alpha=0.05) to detect <40% successful completion of ferumoxytol injection treatment.

### **10 Source Documents and Access to Source Data/Documents**

Source data are all information, original records of clinical findings, observations, or other activities in a clinical study necessary for the reconstruction and evaluation of the study findings. Source data are contained in source documents. Examples of these original documents, and data records include: hospital records, clinical and office charts, laboratory notes, memoranda, subjects' diaries or evaluation checklists, pharmacy dispensing records, recorded data from automated instruments, copies or transcriptions certified after verification as being accurate and complete, microfiches, photographic negatives, microfilm or magnetic media, x-rays, subject files, and records kept at the pharmacy, at the laboratories, and at medico-technical departments involved in the clinical trial. It is acceptable to use CRFs as source documents. If this is the case, it should be stated in this section what data will be collected on CRFs and what data will be collected from other sources.

The study case report form (CRF) is the primary data collection instrument for the study. All data requested on the CRF will be recorded. All missing data will be explained. If a space on the CRF is left blank because the procedure was not done or the question was not asked, "N/D" will be recorded. If the item is not applicable to the individual case, "N/A" will be recorded. All entries will be printed legibly in black ink. If any entry error has been made, a single straight line will be drawn through the incorrect entry and enter the correct data above it. All such changes will be initialed and dated. For clarification of illegible or uncertain entries, the clarification will be printed above the item, then initialed and dated.

Access to study records will be limited to IRB-approved members of the study team. The investigator will permit study-related monitoring, audits, and inspections by the IRB/EC, the sponsor, government regulatory bodies, and University compliance and quality assurance groups of all study related documents (e.g. source documents, regulatory documents, data collection instruments, study data etc.). The investigator will ensure the capability for inspections of applicable study-related facilities (e.g. pharmacy, diagnostic laboratory, etc.).

Participation as an investigator in this study implies acceptance of potential inspection by government regulatory authorities and applicable University compliance and quality assurance offices.

CONFIDENTIAL

This material is the property of the NYU School of Medicine and Langone Medical Center. Do not disclose or use except as authorized in writing by the study sponsor  
Interventional Template Version: 28 APR 2017

## **11 Quality Assurance and Quality Control**

QC procedures will be implemented beginning with the data entry system and data QC checks that will be run on the database will be generated. Any missing data or data anomalies will be communicated to the site(s) for clarification/resolution.

Following written SOPs, the monitors will verify that the clinical trial is conducted and data are generated, documented (recorded), and reported in compliance with the protocol, GCP, and the applicable regulatory requirements (e.g., Good Laboratory Practices (GLP), Good Manufacturing Practices (GMP)).

## **12 Ethics/Protection of Human Subjects**

### ***12.1 Ethical Standard***

The investigator will ensure that this study is conducted in full conformity with Regulations for the Protection of Human Subjects of Research codified in 45 CFR Part 46, 21 CFR Part 50, 21 CFR Part 56, and/or the ICH E6.

### ***12.2 Institutional Review Board***

The protocol, informed consent form(s), recruitment materials, and all participant materials will be submitted to the IRB for review and approval. Approval of both the protocol and the consent form must be obtained before any participant is enrolled. Any amendment to the protocol will require review and approval by the IRB before the changes are implemented to the study. All changes to the consent form will be IRB approved; a determination will be made regarding whether previously consented participants need to be re-consented.

### ***12.3 Informed Consent Process***

The investigators will comply with applicable regulatory requirements and should adhere to 45 CFR Part 46, 21 CFR Part 50, 21 CFR Part 56, and/or ICH GCP. Prior to the beginning of the trial, the investigator will have the IRB's written approval for the protocol and the written informed consent form(s) and any other written information to be provided to the participants.

#### ***12.3.1 Consent and Other Informational Documents Provided to Participants***

Consent forms describing in detail the study agent, study procedures, and risks are given to the participant and written documentation of informed consent is required prior to starting intervention/administering study product.

CONFIDENTIAL

This material is the property of the NYU School of Medicine and Langone Medical Center. Do not disclose or use except as authorized in writing by the study sponsor  
Interventional Template Version: 28 APR 2017

### **12.3.2 Consent Procedures and Documentation**

The consent process will be conducted by trained IRB-approved personnel during a time of clinical stability in a quiet private room located in the NYULH Clinical Research Center. Extensive discussion of risks and possible benefits of participation will be provided to the participants and their families. Consent forms will be IRB-approved and the participant will be asked to read and review the document. The investigator will explain the research study to the participant and answer any questions that may arise. All participants will receive a verbal explanation in terms suited to their comprehension of the purposes, procedures, and potential risks of the study and of their rights as research participants. Participants will have the opportunity to carefully review the written consent form and ask questions prior to signing. The participants should have the opportunity to discuss the study with their surrogates or think about it prior to agreeing to participate. The participant will sign the informed consent document prior to any procedures being done specifically for the study. The participants may withdraw consent at any time throughout the course of the trial. A copy of the signed informed consent document will be given to the participants for their records. The rights and welfare of the participants will be protected by emphasizing to them that the quality of their medical care will not be adversely affected if they decline to participate in this study.

A copy of the signed informed consent document will be stored in the subject's research record. The consent process, including the name of the individual obtaining consent, will be thoroughly documented in the subject's research record. Any alteration to the standard consent process (e.g. use of a translator, consent from a legally authorized representative, consent document presented orally, etc.) and the justification for such alteration will likewise be documented.

### **12.4 Participant and Data Confidentiality**

All patient data will be kept strictly confidential, except when published for purposes of reporting data. In that case, the patients are never identified. All electronic data will be de-identified and transmitted and stored with secure systems that meet or exceed Federal guidelines (REDCap). The Principal Investigator will maintain files with identifying information in a locked cabinet in a locked room or in password-protected files on a password-protected computer. No vulnerable subject populations will be enrolled in this study.

Information about study subjects will be kept confidential and managed according to the requirements of the Health Insurance Portability and Accountability Act of 1996 (HIPAA). Those regulations require a signed subject authorization informing the subject of the following:

- What protected health information (PHI) will be collected from subjects in this study
- Who will have access to that information and why
- Who will use or disclose that information
- The rights of a research subject to revoke their authorization for use of their PHI.

In the event that a subject revokes authorization to collect or use PHI, the investigator, by regulation, retains the ability to use all information collected prior to the revocation of subject authorization. For subjects that have revoked authorization to collect or use PHI, attempts should be made to obtain permission to collect at least vital status (i.e. that the subject is alive) at the end of their scheduled study period.

Participant confidentiality is strictly held in trust by the participating investigators, their staff, and the sponsor(s) and their agents. No information concerning the study or the data will be released to any unauthorized third party without prior written approval of the sponsor.

CONFIDENTIAL

This material is the property of the NYU School of Medicine and Langone Medical Center. Do not disclose or use except as authorized in writing by the study sponsor  
Interventional Template Version: 28 APR 2017

The representatives of the IRB or other governmental regulatory office may inspect all documents and records required to be maintained by the investigator, including but not limited to, medical records (office, clinic, or hospital) and pharmacy records for the participants in this study. The clinical study site will permit access to such records.

The study participant's contact information will be securely stored at each clinical site for internal use during the study. At the end of the study, all records will continue to be kept in a secure location for as long a period as dictated by local IRB and Institutional regulations.

Study participant research data, which is for purposes of statistical analysis and scientific reporting, will be transmitted to and stored at NYU Langone Medical Center. This will not include the participant's contact or identifying information. Rather, individual participants and their research data will be identified by a unique study identification number. The study data entry and study management systems used by clinical sites and by NYU Langone Medical Center research staff will be secured and password protected. At the end of the study, all study databases will be de-identified and archived at the NYU Langone Medical Center.

## 13 Data Handling and Record Keeping

### 13.1 Data Collection and Management Responsibilities

Information about study subjects will be kept confidential and managed according to the requirements of the Health Insurance Portability and Accountability Act of 1996 (HIPAA). A random Study ID code will be assigned to each participant. This code will be used on all written and electronic research records. The Principal Investigator and study coordinator will be able to link the Study ID code back to the personal information during the interval of active participation in the study, but this link will be destroyed after the subject has completed the study procedures. Consent forms, links between Study ID and personal information, paper case report forms, laboratory reports, and other study data will be kept in a project notebook in a locked cabinet in a locked office. Research data without identifiers will be maintained on the NYU School of Medicine REDCap system. The REDCap system provides secure password protected storage of research information behind the NYU firewall and provides quality control and audit trail functions to validate the integrity and quality of the research data. Study data records will be maintained for a minimum of 3 years, or longer if requested by Sponsor.

Data collection is the responsibility of the clinical trial staff at the site under the supervision of the site PI. The investigator is responsible for ensuring the accuracy, completeness, legibility, and timeliness of the data reported.

All source documents will be completed in a neat, legible manner to ensure accurate interpretation of data. Black ink is required to ensure clarity of reproduced copies. When making changes or corrections, the original entry will be crossed out with a single line, and initialed and dated.

Copies of the electronic CRF (eCRF) will be provided for use as source documents and maintained for recording data for each participant enrolled in the study. Data reported in the eCRF derived from source documents should be consistent with the source documents or the discrepancies should be explained and captured in a progress note and maintained in the participant's official electronic study record.

CONFIDENTIAL

This material is the property of the NYU School of Medicine and Langone Medical Center. Do not disclose or use except as authorized in writing by the study sponsor  
Interventional Template Version: 28 APR 2017

